### 2.2 Aims and Objectives

#### Aims

1. To establish the metabolic/molecular response in both adipose tissue and skeletal muscle to acute starvation (~82 h).
2. To establish the sensory experience to prolonged fasting (pain, fatigue, drive).

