### 2.3 Rationale

We plan to study participants before, after and during ~82 hours of no energy intake. Whilst few studies have extended starvation beyond 48-72 h, this duration is sufficient to observe the established shift towards greater reliance on lipids to fuel metabolism [2-5]. Necessarily, extension of the starvation beyond this duration therefore guarantees stability in the reliance on endogenous fuels (e.g. NEFAs, and ketones). At the level of the adipose tissue, an increase in the efflux of NEFA from adipose tissue as well as a reduction in glucose uptake is apparent during the early stages of a prolonged fast (~20 h) [5-7]. Necessarily, given that changes in metabolism within the adipose tissue occur this rapidly, it is surprising that so few studies have included measures of this tissue under conditions of prolonged fasting. In particular, assessment of genes and proteins responsible for regulating substrate metabolism in the adipose tissue would provide interesting insight into the metabolic flexibility of this tissue under severe energy deficit. Furthermore, measurement of amino acids and their respective ketoacids in adipose, skeletal muscle, and the circulation would further our understanding of how these metabolically important tissues respond in order to preserve/maintain skeletal muscle during energy deficit [2, 8].

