Surprisingly, only one study to date has investigated changes in post-prandial metabolism following mixed meal ingestion, as opposed to oral or intravenous tolerance tests [2, 9, 10]. Notably, whilst this study aimed to achieve a 72-h starve, provision of the mixed meal tolerance test immediately prior to beginning the 72-h starvation period resulted in an actual starve duration closer to ~2 days. Given the dramatic effect of acute starvation on gastric emptying [9] it is especially important to investigate the meal responses. Furthermore, given that insulin resistance following prolonged fasting persists even following a 24 h refeed, it would be insightful to include measures of sequential meals (i.e. the response to the standardised lunch and dinner will be assessed via continual glucose monitors). Finally, few, if any, studies have assessed the physical activity response to periods of prolonged fasting. Necessarily, methods such as doubly labelled water would not be appropriate due to the underlying assumptions with RQ as well as only giving a total energy expenditure value. Alternatively, employment of combined heart rate/accelerometry (Actiheart), would be appropriate in order to assess the change in physical activity levels, whilst giving a detailed breakdown in changes in intensity.

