## **2.6 Statistical analysis**

### *Sample estimate:*

Due to the drastic nature of the intervention outlined (i.e. the complete abstinence from energy intake), a relatively small sample size will be required. As such, based on previous research, a sample size of 6-10 participants should be sufficient to observe changes in metabolism with this duration of fast.

Descriptive statistics will be calculated using Microsoft Excel. Normality of data will be assessed using GraphPad Prism 8.0. Repeated measures ANOVA Will be employed to identify significant effects of TREATMENT & TIME for post-prandial data. Paired t-test or Wilcoxon will be used to compare variables assessed only pre-and post-intervention. One-way ANOVA will be used to assess changes in variables assessed each day. Bonferroni post-hoc tests will locate significant differences where they exist. Normalised confidence intervals will be calculated to plot as error bars on figures. The magnitude of these CIs directly infers the difference between means at each time point (i.e. statistical significance) rather than variance of individual values around the mean.

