### 5. Intervention

Participants will be provided with their last meal at ~1900 h on the day of the meal testing. From this point onwards, participants will be asked to refrain from eating for ~82 hours until their return visit to the laboratory. Throughout this period of extended fasting participants will be provided with 80 mmol sodium and 40mmol potassium daily (to consume in the form of slow-release tablets) to minimize the confounding effects of fluid deprivation and intravascular volume depletion on cardiovascular reflexes and sympathetic nervous system activity. Subjects will also be permitted to consume water, non-sugared carbonated drinks

and, with the exception of the day of the pre/post measurements, non-sugared decaffeinated coffee and tea (if they normally consume tea and coffee).

Upon waking each day participants will be asked to assess their urinary ketone levels, blood pressure, and weight. Participants will be asked to repeat this in the evening at 2000 h.

Each day participants will be asked to return to the laboratory to provide a blood sample. On the second day of starvation participants will also be asked to provide a blood sample at 2000 h.

Furthermore, throughout the intervention participants will be asked to wear an actiheart monitor in order to assess physical activity levels in response to prolonged fasting.

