## **7. Ethical considerations of risk and discomfort**

Acute starvation may cause discomfort for participants including headaches and lack of energy. All participants will be supervised by a member of the research team throughout the protocol. Participants who drop out after one day of fasting will not be included in follow up testing, but will be provided with food to break their fast. Conversely, participants who decide to not continue with study following 2 days of fasting will be asked to come in for follow up testing/standardised meal provision. Biopsies also introduce a risk for discomfort for participants but will only be performed by trained and experienced members of staff who follow the guidelines for safe practice. Intravenous cannulation has the potential to cause minor discomfort and bruising. Furthermore, there is a small associated risk of infection and/or embolism, where blood flow to the vein becomes partially restricted. In order to minimise these risks, cannulation will only be carried out by qualified and experienced staff members. The cannula is an essential aspect will only be in the vein for a maximum of 3 hours per laboratory visit, whereas the venepuncture needle on days 1,2, and 3 of the fast will be removed as soon as the sample is obtained.

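### Does the plan need to say whether participants who stop after two days of fasting enter the ~82 h pre/post comparison?

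*Combined protocol and SAP*

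**What the plan says.** Section 7 of the protocol (ethical considerations) treats two kinds of early stopper differently. On the first it says: "Participants who drop out after one day of fasting will not be included in follow up testing". Those who do "not continue with study following 2 days of fasting will be asked to come in for follow up testing/standardised meal provision". The second group therefore has a before and an after value, with a shorter fast in between.

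Section 2.6 lists the tests: repeated measures ANOVA for the post-prandial data, one-way ANOVA for daily variables, and for the rest "Paired t-test or Wilcoxon will be used to compare variables assessed only pre-and post-intervention". It defines no analysis set, completer rule or sensitivity analysis, and no other section does. On numbers it says that "a sample size of 6-10 participants should be sufficient to observe changes in metabolism with this duration of fast".

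Aim 1 in section 2.2 sets the exposure at ~82 h. The clock starts in section 5: "Participants will be provided with their last meal at ~1900 h on the day of the meal testing". Section 6 places the repeat visit at the end of the intervention. Section 2.3 remarks that the one earlier mixed-meal study intended 72 h but its timing "resulted in an actual starve duration closer to ~2 days". The same section accepts 48-72 h as long enough to see the shift towards lipid fuel, and adds that "extension of the starvation beyond this duration therefore guarantees stability in the reliance on endogenous fuels". Section 2.1 says that the work is not hypothesis driven.

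**The concern.** The protocol deliberately collects pre/post pairs after a fast of about two days and then does not say what to do with them. Section 7 points towards including them, because the data are gathered. Sections 5 and 6 point towards leaving them out, because the repeat visit follows a completed ~82 h fast. Section 2.3 sharpens the question, since it sets this study apart from its predecessor partly by the length of fast achieved.

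Both primary outcomes (the meal response, and amino acid metabolism in tissue and blood) are measured at the visit in question. With 6 to 10 participants, one person is 10-17% of the pairs. The study is single-arm and open, so a reading that is not fixed beforehand could be chosen once the results are known. The answer would then describe either ~82 h or a mixture of shorter and full fasts.

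**Working it through.** The sample size of 6-10 cannot be reproduced, because the documents give no alpha, power, effect size, SD or dropout rate. Everything below is therefore for scale and rests on stated assumptions: two-sided 5%, paired t-test, normal within-person differences with SD 1, and 80% power at full n. That power corresponds to a true change of 1.43 SD (n = 6) or 1.00 SD (n = 10).

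**1. Length of the shorter fast.** From ~1900 h, two days is 48 h. Testing at an assumed 0800 h next morning gives 48 + 13 = 61 h. The shortfall is 82 - 61 = 21 h to 82 - 48 = 34 h. Someone who stops during the third day is closer to 82 h.

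**2. How often it arises.** The chance of at least one such pair is 1 - (1 - q)^n, where q is the chance that a person stops in the relevant window. For q = 5%, 10% and 20% it is 26%, 47% and 74% with n = 6, and 40%, 65% and 89% with n = 10. One-day stoppers have no post value and raise no question, so q must exclude them.

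**3. Effect of including the pair.** With k shorter-fast pairs whose change is f times the ~82 h change, the mean relative to the ~82 h change is (n - k + kf)/n.

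| n | k | f = 0.25 | f = 0.5 | f = 0.9 | f = 1.5 |
|---|---|---|---|---|---|
| 6 | 1 | 88% | 92% | 98% | 108% |
| 6 | 2 | 75% | 83% | 97% | 117% |
| 10 | 1 | 93% | 95% | 99% | 105% |
| 10 | 2 | 85% | 90% | 98% | 110% |

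In simulation (200,000 trials per scenario, f from 0.25 to 1.5, n = 6, 8 and 10), the pooled 95% interval covers the ~82 h change in about 93-95% of trials. If the true change is 1.5 or 2 times larger, coverage falls to about 92% in the worst two-stopper cases.

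**4. Effect of leaving it out.** Power falls from 80% to 67% (n = 6) or 75% (n = 10) with one exclusion, and to 50% or 68% with two. The rank test suffers more: with 5 pairs the smallest two-sided exact Wilcoxon p-value is 2/2^5 = 0.0625, so it cannot reach 5%; with 6 pairs it is 2/2^6 = 0.031.

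**5. Do the two readings disagree because of the shorter fast?** With one stopper and f from 0.25 to 1.5, the two t-tests differ on significance in 17-20% of trials at n = 6 and 9-11% at n = 10. At f = 1, where the shorter fast makes no difference at all, they still differ in 16.6% and 9.5%. Most of the disagreement is the cost of losing a pair from a small sample. At 1.5 times the assumed effect it is 5-10% (n = 6) and about 2-3% (n = 10). At twice the effect it is 0.4-2% and at most 0.2%. Two stoppers out of six is worse: 30-38% at the assumed effect, 18-27% at 1.5 times and 5-14% at twice.

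**6. Choosing the reading afterwards.** With no true change, the chance that at least one of the two tests is significant is 7.1% (n = 6) or 6.6% (n = 10) with one stopper, and 8.1% or 7.4% with two. Each reading fixed in advance holds about 5%.

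**The case for a change.** The strongest case for a change is that a rule costs one sentence, and that the protocol itself expects stopping and itself notes the short fast of the earlier study. Section 2.6 uses significance tests and section 2.5 names primary outcomes, so the exploratory label does not remove the question of which fast the change belongs to. The acceptance of 48-72 h in section 2.3 concerns fuel use, not the meal response or tissue amino acids. With two stoppers out of six, the readings could diverge materially.

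Much of this stands. The documents do not settle the point, and the choice should not depend on the results. But the case does not show that either reading is wrong. Pooling answers the question for everyone tested, with a modest shift in most scenarios. Completers-only matches the aim more closely, at a price in power and in selection. Section 2.3 describes the earlier study's shortfall without calling two-day data unusable. The error inflation also presumes an analyst who reports whichever result is significant and says nothing of the other.

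**Conclusion.** No change follows. This is missing detail that matters only if someone stops after two days but before ~82 h, and that a careful analyst can handle on meeting it. With so few participants, each shorter fast is visible individually, and the report can state how many pairs were used and how long each person fasted.

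For one such participant the size is modest under either choice: a mean change lowered by 1.7-8.3% (n = 6) or 1.0-5.0% (n = 10) if the two-day change is 50-90% of the full one, against power of 67% or 75% in place of 80% if the pair is dropped. Two stoppers out of six with a much smaller two-day change would matter more (mean lowered by 25% at f = 0.25), but dropping both would leave four pairs and about 50% power, so a written rule would not rescue that case.

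These figures rest on assumed stopping rates, effect ratios and 80% power, none of which the documents give. They also come from the paired t-test, whereas the meal response is planned for repeated measures ANOVA. The reasoning carries over to that analysis, but the exact percentages may not.

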**2.4 Study design**

This study will employ a single-arm, non-randomised design in which participants will act as their own control prior to undergoing 3 days of starvation. The control phase includes ~3 days of habitual energy balance assessment before coming into the laboratory for baseline metabolic and anthropometric assessment. Participants will be provided with monitoring equipment throughout the 3 days of starvation and will be asked to provide a blood sample as well as record their blood pressure, weight, and urinary ketones each day. On the middle day participants will also be asked to come into the lab to provide a blood sample at 2000 h.

**Figure 1.** Protocol schematic depicting the study design.

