### *Secondary*

Change in circulating glycerol and FFAs across the prolonged fast (indices of lipolysis from adipose tissue)

Change in Autophagy (in skeletal muscle and neutrophils)

Total nitrogen (or at least urea nitrogen) in urine (24h collection) throughout the fast (or at least 1st vs last day)

Change in plasma lactate and pyruvate in response to prolonged fasting (indices of Cori cycle)

Change in urinary (acetoacetate), and circulating (beta-hydroxybutyrate) ketones in response to prolonged fasting.

Change in body mass, pre-post, and during the prolonged fast.

Change in blood pressure pre-post, and during the prolonged fast.

Change in waist-hip circumferences pre-post the prolonged fast.

Change in sensory experience (pain, fatigue, drive) in response to prolonged fasting.

Change in haematocrit/haemoglobin pre-post the prolonged fast.

Change in grip strength pre-post the prolonged fast.

Change in reaction time pre-post the prolonged fast.

Change in aspects of immune function and infection risk

Change in interstitial fluid glucose concentrations pre-, post-, and during the prolonged fast (assessed via continual glucose monitoring)

Occurrence of adverse events (e.g. nausea, vomiting, migraines)

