#### Inclusion criteria

- Body mass index 20.0-29.9 kg·m^-2
- Age 18-45 years
- Willing to abstain from food intake for just over 3 days (~82 hours)
- Able and willing to provide informed consent and safely comply with study procedures
- Females to maintain record of regular menstrual cycle phase or contraceptive use
- No anticipated changes in lifestyle during the study (e.g. holidays or exercise programmes)

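### Variables measured daily on the same 6-10 people are assigned a one-way ANOVA with no repeated-measures term, so the stated test uses the wrong error term and may miss modest within-person changes

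*Combined protocol and SAP*

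**What the plan says.** Section 2.6 assigns three analyses to three kinds of data.

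- Meal-test data: "Repeated measures ANOVA Will be employed to identify significant effects of TREATMENT & TIME for post-prandial data".
- Variables measured only before and after the fast: a paired t-test or its Wilcoxon counterpart.
- Daily variables: "One-way ANOVA will be used to assess changes in variables assessed each day".

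The first two name a within-person method; the third does not. Nowhere do the documents give a participant term, a mixed model or a sphericity correction for the daily data.

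The daily data are within-person. Section 2.4 describes a "non-randomised design in which participants will act as their own control". Section 5 says "Upon waking each day participants will be asked to assess their urinary ketone levels, blood pressure, and weight", with a repeat in the evening, and "Each day participants will be asked to return to the laboratory to provide a blood sample". The secondary outcomes in section 2.5 include "Change in body mass, pre-post, and during the prolonged fast", and blood pressure is listed in the same way.

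Section 7 adds that "participants who decide to not continue with study following 2 days of fasting will be asked to come in for follow up" testing, so a daily series can be incomplete. Section 2.6 has no rule for that.

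**The concern.** An ordinary one-way ANOVA assumes that the observations on different days come from different people. Here they come from the same people, and the lasting differences between those people have nothing to do with the fast. Leaving that variance in the error term gives up the main advantage of an own-control design, which matters most with 6-10 participants.

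At stake is the day-by-day part of body mass, blood pressure and ketones, and of any analyte assayed in the daily samples, such as glycerol and free fatty acids. A real and consistent change could be reported as not significant. The meal-response primary outcome and the outcomes measured only before and after the fast are unaffected. The circulating amino-acid primary is affected only if it is assayed in the daily samples, which the documents do not state.

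**Working it through.** **Inputs from the documents.** n = 6-10 (section 2.6); the same participants on every day (sections 2.4 and 5); BMI criterion "Body mass index 20.0-29.9" (section 3).

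**Assumed, because the documents give none.** Alpha 0.05; k = 4 daily time points (3 and 5 also tried); normal data; equal correlation between days (ICC 0.3 to 0.9); a linear change over the days, expressed in SDs of a single measurement. Section 2.6 gives no power, SD or effect size for its 6-10, so there is no figure of the plan's own to reproduce.

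**Error terms.** Set the total variance to 1, of which ICC lies between people.

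- One-way: F on k-1 and k(n-1) degrees of freedom; expected error mean square = ICC + (1 - ICC) = 1.
- Repeated measures: F on k-1 and (k-1)(n-1) degrees of freedom; expected error mean square = 1 - ICC.

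The one-way error is therefore too large by a factor of 1/(1 - ICC): 1.4 at ICC 0.3, 2 at 0.5, 3.3 at 0.7 and 10 at 0.9.

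**Power.** 20,000 simulated trials per setting, with Greenhouse-Geisser epsilon estimated in each trial. One-way v repeated measures, n = 8, k = 4:

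| Change, first to last day | ICC 0.3 | ICC 0.5 | ICC 0.7 | ICC 0.9 |
|---|---|---|---|---|
| 1 SD | 29 v 37% | 24 v 51% | 21 v 78% | 18 v 100% |
| 1.5 SD | 69 v 76% | 68 v 90% | 68 v 99% | 67 v 100% |
| 2 SD | 94 v 96% | 95 v 99% | 95 v 100% | 95 v 100% |
| 3 SD | 100 v 100% | 100 v 100% | 100 v 100% | 100 v 100% |

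- Change needed for 80% power at n = 8: one-way 1.66 SD at every ICC; repeated measures 1.56, 1.32, 1.02 and 0.59 SD at ICC 0.3, 0.5, 0.7 and 0.9.
- n = 6, 1 SD: from 19 v 22% (ICC 0.3) to 12 v 98% (ICC 0.9).
- n = 8, 1 SD, ICC 0.7 with other numbers of days: 26 v 80% (k = 3) and 19 v 77% (k = 5).

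**No true change, n = 6-10.** The one-way test rejects 0-1.9% of the time against a nominal 5%. The Greenhouse-Geisser test is itself somewhat conservative here, at about 2.3-3.4%.

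**Body mass, as an illustration only.** At one assumed height of 1.72 m the BMI range spans 20.0 × 1.72² = 59 kg to 29.9 × 1.72² = 88 kg. If evenly spread, the between-person SD is (29.9 - 20.0) × 1.72² / √12 = 8.5 kg. Assume also a within-person SD of 0.5 kg and a 3 kg linear loss. For n = 8, k = 4:

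- The day means lie -1.5, -0.5, 0.5 and 1.5 kg from their average; the squares sum to 5.
- Expected mean square for days = 8 × 5 / 3 + 0.25 = 13.6.
- One-way error = 8.5² + 0.5² = 72.5, so F is about 13.6 / 72.5 = 0.19. The 5% critical value on 3 and 28 degrees of freedom is 2.95.
- Repeated-measures error = 0.25, so F is about 13.6 / 0.25 = 54. The critical value on 3 and 21 degrees of freedom is 3.07, and 5.59 under the severest sphericity correction (1 and 7).

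Simulated power for n = 6-10 is about 0.1% or less v 100%. With a between-person SD of 5 kg it is about 1% v 100%.

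**The case against.** The best counter-argument concerns the reading. The meal-test sentence covers two factors and the daily variables have one, so one-way may simply count factors. Every other test in the paragraph is within-person, and the normalised confidence intervals planned for the figures also reflect within-person thinking. An unpaired test for the daily data alone would be out of character. This stands as a real possibility. However, the intervals are a plotting rule and supply no test, and the wording still permits two analyses with very different results.

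Three points on weight also stand. The outcomes certain to be affected are secondary ones, in a study that section 2.1 says is not hypothesis-driven. The loss depends on assumed values: it is small at low correlation and disappears for very large changes, which the plan may expect from so drastic an intervention, ketones perhaps among them. And the direction is conservative, although that was checked only for normal data with equal variances and equal correlation between days.

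The missing-day rule is a separate gap and adds nothing to the case on the error term. It is raised because the same sentence can settle it.

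**Conclusion.** The concern holds. Run as written, the test for daily variables uses the wrong error term for own-control data. The cost is power, and it falls on variables whose change is modest relative to the spread between people: body mass is the clearest candidate and blood pressure a possible one. For 8 people and a 1 SD change, the shortfall runs from 8 percentage points (ICC 0.3) to 82 (ICC 0.9). At 2 SD it is 5 points or fewer. These sizes rest on assumed correlations, effect sizes and numbers of days. The existence of the fault does not, provided measurements on the same person are positively correlated. Whether the authors intended the unpaired test cannot be settled from the text, so confidence is moderate. It should be fixed before analysis.

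**What to change.** Replace the sentence on daily variables in section 2.6 with wording such as:

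> Variables measured daily will be analysed by one-factor repeated-measures ANOVA, with participant as the matching factor and Greenhouse-Geisser correction, or by a mixed model with a random participant effect if any day is missing. Post-hoc comparisons between days will be paired and Bonferroni-corrected.

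The cost is one sentence, with no new data, visits or participants. If repeated measures was already intended, this is only a clarification.

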### 4. Trial days

3 days prior to the first experimental visit participants will visit the laboratory to be fitted with a continual glucose monitor, an actiheart activity monitor, as well as a food diary and food scales. They will be asked to record energy intake and to standardise physical activity, caffeine, and alcohol intake.

Upon finishing the 3 days of lifestyle standardisation participants will enter the laboratory for where weight, height, waist:hip circumference, sagittal-abdominal diameter, and skin-fold will be assessed prior to assessment of resting metabolic rate, blood pressure and urinary ketones. Participants will also undergo grip strength, reaction time, and sensory experience assessment. Following this, samples of skeletal muscle and adipose tissue will be collected from the *vastus lateralis* and abdominal adipose tissue respectively. An intravenous cannula will then be placed a 10 mL blood samples will be drawn before ingestion of a carbohydrate rich porridge breakfast (7.3 mg carbohydrate·kJ).

A 3-hour postprandial period follows the ingestion of breakfast with blood samples will be collected at 15, 30- and 60-minute intervals during the first, second and third hour respectively alongside hourly expired gas samples and assessment of subjective appetite and mood. Upon completion of the 3-hour post-breakfast period, participants will have completed the visit and will be provided with a standardised lunch and dinner. Participants will also be provided with urinary ketone sticks, a blood pressure monitor, a set of weighing scales, as well as an actiheart monitor.

Participants will be asked to assess urinary ketones using provided assessment sticks in the evening at 2000 h.

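### Daily blood ketones go to one-way ANOVA with no transformation or unequal-variance method, so post-hoc tests may miss the first rise if spread grows with level

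*Combined protocol and SAP*

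**What the plan says.** The combined protocol and SAP lists this among its secondary outcomes (section 2.5): "Change in urinary (acetoacetate), and circulating (beta-hydroxybutyrate) ketones in response to prolonged fasting". Section 5 has participants give blood every day of the fast, with an extra sample at 2000 h on the second day, and test their urine on waking and at 2000 h. On the urine method, section 4 says: "Participants will also be provided with urinary ketone sticks".

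Section 2.6 assigns methods by measurement schedule:

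- Post-prandial data: "Repeated measures ANOVA Will be employed to identify significant effects of TREATMENT & TIME for post-prandial data".
- Pre/post variables: "Paired t-test or Wilcoxon will be used to compare variables assessed only pre-and post-intervention".
- Daily variables: "One-way ANOVA will be used to assess changes in variables assessed each day".
- Post-hoc tests: "Bonferroni post-hoc tests will locate significant differences where they exist".
- Distribution check: "Normality of data will be assessed using GraphPad Prism 8.0".

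The rank alternative belongs to the pre/post sentence only. For daily variables the plan does not say what follows if normality fails, on which scale the data are analysed, what happens if variances differ between days, or which error term the Bonferroni tests use. It does not say how stick readings are scored.

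**The concern.** ANOVA with a pooled error assumes similar spread at every time point. A concentration that starts near zero and climbs many-fold will often break that assumption, because people who differ by a similar percentage differ by far more in absolute terms once levels are high. The pooled error then reflects the last days, and the comparison of the first rise with pre-fast is judged against a noise level that does not belong to it.

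What is at stake is timing. The post-hoc tests are there to locate change, and daily sampling is what lets them do so. An early rise reported as not significant would place the fuel switch later than it occurred. With 6-10 participants, leaving the scale to be chosen after the data are seen also adds avoidable analytic freedom.

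**Working it through.** **Plan's own figure.** The only number to reproduce is the sample size: "a sample size of 6-10 participants should be sufficient to observe changes in metabolism with this duration of fast". No alpha, power, effect size or SD accompanies it, so it cannot be re-derived.

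**Inputs from the documents.** n = 6-10; one-way ANOVA with Bonferroni; last meal at ~1900 h; daily blood samples. The plan does not list the analytes run on each daily sample; I take beta-hydroxybutyrate to be among them.

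**Assumed inputs (none in the documents).** Log-normal beta-hydroxybutyrate, medians in mmol/L as shown below, two-sided alpha 0.05.

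**Hand calculation.** Four samples with medians 0.1, 0.3, 1.5, 3.5; log-scale SD 0.4 between and 0.3 within persons, so total √(0.4² + 0.3²) = 0.5; n = 8; Bonferroni over all 6 pairs.

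- Raw mean = median × exp(0.5²/2) = median × 1.133: 0.113, 0.340, 1.700, 3.966.
- Raw SD = mean × √(exp(0.5²) − 1) = mean × 0.533: 0.060, 0.181, 0.906, 2.114.
- Pooled variance = (0.004 + 0.033 + 0.821 + 4.468)/4 = 1.331, SD 1.154. The last sample supplies 4.468/5.325 = 84% of it.
- Raw scale, pooled: difference 0.227; SE = 1.154 × √(2/8) = 0.577; ratio 0.39 against a critical t of 2.84 (28 df).
- Log scale, pooled: ln 3 = 1.099; SE = 0.5 × √(2/8) = 0.25; ratio 4.39 against the same 2.84.
- Raw scale, own SD: SD of the paired difference 0.152; SE = 0.152/√8 = 0.0537; ratio 4.22 against 3.64 (7 df).
- Log scale, own SD: SE = 0.3 × √(2/8) = 0.15; ratio 7.32 against 3.64.

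With a flatter profile (0.1, 1, 1.5, 2) the pooled raw SD is 0.814, the SE 0.407 and the difference 1.020. The ratio is 2.51, close to the critical value, so the test is no longer hopeless.

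**Simulation 1.** Power for pre-fast versus first real rise; ordinary one-way pooled error; Bonferroni over all pairs; n = 6, 8, 10; between/within-person CV 30/20%, 40/30%, 50/40%.

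| Medians | Raw | Log |
|---|---|---|
| 0.1, 0.3, 1.5, 3.5 | 0% | 64-100% |
| 0.1, 0.5, 2, 4 | 0% | 96-100% |
| 0.1, 1, 2.5, 4 | 0-29% | 100% |
| 0.1, 0.1, 1, 2.5, 4 (rise at third sample) | 1-38% | 100% |
| 0.1, 1, 1.5, 2 | 13-98% | 100% |

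Raw scale with pair-specific error: 29-100% across these profiles. Overall raw-scale test of time: 92-100%.

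**Simulation 2.** Medians 0.1 pre-fast, 0.2-0.6 on day 1, 3.5-5 at the end; log SD 0.3-0.4 between and within persons; n = 6-10; alpha 0.05/5 = 0.01. Pooled one-way error: 0% raw, about 25-100% log. Own SD: about 16-99.8% raw, 32-100% log. The log scale was at least as good in every scenario. A flatter profile gave 11-94% with pooled raw error.

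**Sticks.** With readings simulated as grades 0-5, overall power was 100% by ANOVA and by Friedman. The smallest exact two-sided Wilcoxon p is 2/2⁶ = 0.031 at n = 6 and 2/2⁷ = 0.016 at n = 7, both above 0.05/5 = 0.01.

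**The case against.** A reader might infer that the plan makes the early rise undetectable. The documents do not support that. The overall test has 92-100% power, pooled raw-scale power reaches 98% for the flattest profile, and comparisons with their own SD recover much of the loss without logs. The error term is unstated, so the 0% figure describes one permitted reading of the plan.

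A reader might also infer that the plan prescribes raw-scale analysis. It is silent on scale. Normality is to be checked, and a transformation might follow. The silence is the gap, but it is not a stated wrong method.

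The premises about ketones come from outside the documents: the many-fold rise, spread growing with level, and any grading of stick readings. They are plausible and labelled here as assumptions. Because the data were simulated as log-normal, the log analysis is favoured by construction.

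Timing also matters. The hour of the daily sample is not given. A morning sample would fall ~12 h after the last meal and might not differ from the overnight-fasted baseline; where no rise was simulated there, rejection was about 0-1% on either scale, as it should be. The question then moves to the next sample.

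For sticks, it is tempting to say that ANOVA hides the rise or that a top grade would look like a plateau. The simulation showed no loss of the overall rise, and the documents mention no top grade. Pairwise rank tests would be no remedy, since at n = 6-7 none could reach significance over five comparisons.

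Finally, this is one of many secondary outcomes in a study that section 2.1 says is not hypothesis driven. That limits the consequence but does not remove the gap.

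**Conclusion.** The point holds in a limited form. For daily blood ketones the plan specifies neither a scale nor protection against unequal variances. If beta-hydroxybutyrate rises many-fold with spread proportional to level, and the post-hoc error is pooled, the first real rise may be missed. The cost ranges from nearly all the power, when that rise is small against later values, to little for the flattest profile at low variability and n = 10. It comes from pooling unequal variances more than from the raw scale alone. The general rise in ketones is not at risk, and no harm is shown for the overall analysis of stick readings. For FFA and glycerol the gain from logging would be smaller. A modest weakness, worth correcting because the better method is almost free.

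**What to change.** Add to section 2.6:

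> Circulating beta-hydroxybutyrate is log-transformed (values below the detection limit set by a stated rule) and analysed in a within-subject (repeated-measures) model. Each time point is compared with pre-fast using that comparison's own SD, with Bonferroni adjustment, and reported as a fold change with 95% CI. Blood beta-hydroxybutyrate is the quantitative ketone measure. Urine stick readings, if recorded as grades, are shown as counts per grade with an overall Friedman test and no pairwise tests.

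State the hour of the daily blood sample as well, so that the first comparison can be interpreted. The cost is a few sentences and minutes of analysis, with no change to study procedures. The downside is that results become fold changes rather than absolute differences; raw medians by day can be shown beside them.
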